#### Cross-sectional prevalence survey (WP2) 4.4

WP-2 is a cross-sectional prevalence survey which is the first of its kind to attempt recruitment at a primary care network level (PCN). Each general practice within PCNs, SAPA5 and The Foundry, will individually sign a research agreement, but the delivery of the research in terms of participant selection and approach will be delivered at a network level. The study will look to recruit patients over a three-year period using the Burden of Obstructive Lung Disease (BOLD) methodology, which has been used in multiple international settings globally to conduct COPD prevalence studies.

## Sample size:

The two PCN patient registers will be randomly sampled to obtain 4,761 people >35year, these people will be invited to participate in the study and undergo a breathing assessment. The BLISS cohort study (NIHR Programme grant) had a 30% uptake following a postal invitation. Anticipating a 30% uptake, 1,428 people will undergo a breathing assessment and assuming a 7% prevalence, a cohort of 100 patients with COPD from underserved communities will be recruited. This would allow a prevalence estimate with ±4-5% precision for a 95% confidence interval. This would be sufficient to compare with and validate model estimates from WP1, and allow comparison with registered COPD diagnoses from the COPD QOF register

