# 11.1.3 Quantitative cross-sectional prevalence survey (WP-2)

There will cross-sectional survey data on all participants randomised into the study, 1428 participants will be offered a breathing assessment and cross-sectional prevalence data will be available for each participant and captured on RedCAP electronic data capture held on a secure university server.

The following raw quantitative data will be generated from the cross-sectional prevalence survey:

- Categorical demographic: sex, ethnicity •
- Numerical demographic: DOB, height, weight,
- Numerical spirometry values (e.g. FEV1, FVC), dyspnoea scores and exacerbation frequency
- Numerical laboratory test results: full blood counts
- Categorical chest xray data

These data will be predominantly numerical but include some categorical. They will be entered into RedCAP an electronic data capture software and stored on a University the Sheffield server on the X:drive. It will then be exported as a .csv file for interrogation and further analysis in R.

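### The ±4-5% precision stated for the WP2 prevalence does not follow from 1,428 people assessed at 7% prevalence, which gives about ±1.3 percentage points

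*Protocol*

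**What the plan says.** Under Sample size in section 4.4, the protocol sets out a recruitment chain and then a precision. The chain starts with the sample: "The two PCN patient registers will be randomly sampled to obtain 4,761 people >35year". It continues: "Anticipating a 30% uptake, 1,428 people will undergo a breathing assessment and assuming a 7% prevalence". It ends with the expected yield: "a cohort of 100 patients with COPD from underserved communities will be recruited". The next sentence gives the precision: "This would allow a prevalence estimate with ±4-5% precision for a 95% confidence interval". The paragraph closes by calling this enough to compare with and validate the WP1 model and to compare with diagnoses on the QOF register.

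No formula, denominator, design effect or subgroup is given for the ±4-5%. Section 8.1, under Bias and Representation, describes random selection of individual patients from the network lists, so no cluster sampling is described.

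The Study Summary agrees with section 4.4: 4,761 people sampled and offered an assessment, 30% uptake and 100 patients with COPD. Section 11.1.3 words the same number differently: "1428 participants will be offered a breathing assessment".

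**The concern.** The sampling precision of a prevalence depends on how many people are assessed, here 1,428, and not on how many cases are found among them. A half-width of 4 to 5 points is far too wide for a sample of that size at 7%. The sentence follows directly after the cohort of 100, which suggests that the number of cases was taken as the sample size.

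This is the only precision statement for the survey, and the sufficiency claim is built on it. Read at face value, 7% ±4-5 points runs from about 2-3% to 11-12%. That range contains both prevalences from which section 2.3 argues underdiagnosis: 4.5% diagnosed in UK people over 40, and 10.1% across the 12 international sites. A reader relying on the sentence would doubt that the survey can do what the next sentence claims. The stated precision also cannot explain the sample size, because it needs only about a tenth as many assessments.

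**Working it through.** **Inputs, all from section 4.4, Sample size:** 4,761 invited; 30% uptake; 1,428 assessed; 7% prevalence; 100 cases; 95% confidence.

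**1. The recruitment chain reproduces.** 4,761 × 0.30 = 1,428.3, and 1,428 × 0.07 = 99.96. Working backwards, 100 / 0.07 / 0.30 = 4,762. The counts are sound.

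**2. The precision does not reproduce.** Half-width = 1.96 × √(p(1−p)/n).

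- With p = 0.07 and n = 1,428: 1.96 × √(0.07 × 0.93 / 1,428) = 1.96 × 0.00675 = 0.0132, or ±1.32 points (5.7% to 8.3%).
- The Wilson half-width is 1.33 points. The exact (Clopper-Pearson) interval for 100/1,428 is 5.7% to 8.5%, half-width 1.36.
- Ratio of stated to recomputed: 4/1.32 = 3.0 and 5/1.32 = 3.8.

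**3. What sample size would give ±4-5 points?** n = 1.96² × 0.07 × 0.93 / d².

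- d = 0.05: n = 100.
- d = 0.04: n = 156.

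So n = 100 at 7% gives ±5.0 points. The 4% end does not come from 100 people at 7%. It needs either 156 people, a number that appears nowhere in the protocol, or n = 100 with a prevalence near 4.5% (±4.06).

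**4. Other readings tried.**

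| Reading | Half-width |
|---|---|
| 99% confidence, n = 1,428, p = 7% | ±1.74 points |
| Finite population correction (94,656 registered) | ±1.31 points |
| Worst case p = 50%, n = 1,428 | ±2.59 points |
| Design effect 2 (assumed) | ±1.87 points |
| Design effect 5 (assumed) | ±2.96 points |
| Uptake of only 5% (238 people), p = 7% | ±3.24 points |
| Relative to 7% | 1.32/7 = ±19% |
| Proportion undiagnosed among 100 cases, at 50% | ±9.8 points |

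For 1,428 people to give ±4 to ±5 points at 7%, the design effect would have to be (4/1.32)² to (5/1.32)², about 9 to 14.

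**5. By network, under an assumption.** Section 4.2 gives lists of 58,100 (The Foundry) and 36,556 (SAPA5). If the 1,428 split in that proportion, about 877 and 551 are assessed, giving ±1.69 and ±2.13 points at 7%. The lists cover all patients, not only those over 35, and the protocol does not state an allocation.

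**The case against.** The best defence is that the error is on the safe side. The planned sample delivers more than the sentence promises, and no recruitment number changes. That stands, and it rules out one tempting inference: that the survey is too small, or could show neither underdiagnosis nor agreement with the model. That inference treats the misstated figure as the achieved precision. The two prevalences in section 2.3 are also not the survey's stated comparators, which are the WP1 estimates and the QOF register, and the protocol sets no margin for validation.

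The cause is also not proven. A reader might infer that the 100 cases were certainly used as the denominator. No derivation is shown, and at 7% that explanation reaches only the 5% end. A rival exists: worst-case p = 50% with about 384 to 600 people gives ±5.0 to ±4.0, and SAPA5 alone at about 551 would give ±4.2. The text does not describe this either, and it conflicts with the assumed 7%. The cause is therefore probable only.

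A reader might also take section 11.1.3 literally and apply 30% uptake to the 1,428. The explicit chain from 4,761 to 1,428 to 100 in section 4.4, which the Study Summary supports, rules this out. Section 11.1.3 is loose wording about the same 1,428 people.

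None of this rescues the ±4-5%, because no whole-sample reading tried in the working reaches it.

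**Conclusion.** The stated precision is wrong as written. On the protocol's own figures the 95% half-width for the overall prevalence is about ±1.3 percentage points, not ±4-5. The misstatement is by a factor of about three to four, and it understates what the design achieves. The sample size of 4,761 invited and 1,428 assessed can stay. What fails is the link between the number and the claim: the sufficiency statement rests on a wrong figure, and ±4-5 points at 7% would need only about 100 to 156 assessments.

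The ±1.3 points assumes individual random sampling, 30% uptake, 7% prevalence and no design effect. It is sampling error only and should not be read as the total uncertainty. It does not cover bias from non-response at 30% uptake, or from limiting spirometry to people with symptoms (section 4.4, Recruitment and screening). Nor does it describe the precision of subgroup estimates or of the proportion undiagnosed among about 100 cases.

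**What to change.** - **Section 4.4, Sample size.** Replace the precision sentence with: *With 1,428 people assessed and 7% prevalence, the 95% CI half-width is about ±1.3 percentage points (sampling error only; it does not cover bias from non-response or from limiting spirometry to symptomatic people).*
- **Same paragraph.** State the 100 cases separately, as the expected cohort for WP3/4, so that they are not read as the basis of the precision.
- **Section 11.1.3.** Align with the Study Summary and section 4.4: 4,761 invited, about 1,428 expected to undergo assessment.
- **Network-level precision, if wanted.** Give about ±1.7 points for The Foundry and ±2.1 for SAPA5 only if the allocation between the networks is stated as an assumption.

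The cost is a wording change in two sections. Sample size, recruitment and procedures are unchanged.

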## Recruitment and screening for COPD:

The random sample of 4,761 people (40/week) will initially be telephoned (using interpreting services if their registered language is not English) and invited to participate in the study. This initial approach will be conducted by a PCN administrator (and then a follow-up call made by the research team only to those who are interested in participating and informed consent obtained.

A breathing assessment will then be arranged by the study team within the PCN, at a medical practice which patients are familiar. The breathing assessment will include a validated symptom-based questionnaire and in those that are symptomatic the following:

- Quality assured post-bronchodilator spirometry
- Chest radiograph
- Full blood count

The definition of COPD by the Global Initiative for Obstructive Lung Disease (GOLD) 2023 report will be used. A fixed post bronchodilator FEV1/FVC ratio <0.7 will be used to establish the diagnosis of COPD as per GOLD guidance.

Interpreters will be used for patients whom their registered language is not English, and home visits conducted for housebound patients where possible. De-centralising and offering assessment within general practice settings may be necessary. To maximise recruitment, a flexible approach will be taken, modifying the breathing assessment offer if uptake is low, within the limits of the capacity of the research team.

Consent will be obtained for details to be held as part of a COPD cohort for approaching for recruitment into the qualitative interview study in **WP3 & 4**, as well as offering other potential opportunities for further involvement in future research work.

Only 1/5th of patients diagnosed as part of the Target COPD screening trial in the BLISS Cohort study were entered on to general practice COPD Quality and Outcomes (QOF) registers post study. To maximise engagement of general practices, and to ensure timely diagnosis impacts patients care we will ensure that all COPD QOF targets (recorded number of exacerbations in the previous 12mths, Medical Research Council (MRC) Dyspnoea Scale, if MRC Dyspnoea scale is  $\geq$  3 referred to pulmonary rehabilitation) are met for patients diagnosed with COPD in the study. This has been discussed with PCN managers and local practice partners.

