#### 3.2 **Objectives**

Estimate the number of people with undiagnosed COPD in underserved populations in England (WP1)

Determine the actual prevalence of undiagnosed COPD in an underserved primary care populations (WP2).

Understand barriers and facilitators to recognising COPD in underserved populations (WP3).

Understand how COPD and its primary care interventions (smoking cessation, pulmonary rehabilitation, and vaccination) are perceived in underserved populations (WP4).

Co-develop interventions to improve uptake of primary care interventions (smoking cessation, pulmonary rehabilitation, and vaccination) for COPD in underserved populations (WP5)

### STUDY DESIGN/ METHODS 4

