# Data Analysis:

Regression analysis will be used to predict expected COPD prevalence in each general practice in England, based on the prevalence of risk factors (e.g. tobacco dependency, poor housing, age and deprivation) and their magnitude of association with COPD from published literature. These expected COPD rates will be compared with NHS digital actual prevalence data in general practices from COPD QOF registers. This will allow estimated to be made of the shortfall in COPD diagnosis nationally at a general practice level. Factors that may be associated with underdiagnosis of COPD such as the percentage of patients from ethnic minority backgrounds will be explored. The model estimates of COPD prevalence will also be compared with the 2010 Health Survey for England Data on respiratory and lung health which included a subset of people who underwent spirometry to diagnose COPD.

As this will utilise routinely collected data already in the public domain no formal ethical approval is required to conduct this work.

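### Spirometry is limited to symptomatic attendees, so WP2 can estimate only symptomatic COPD, while its objective and sample size are written for COPD without that limit

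*Protocol*

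**What the plan says.** - **Who is tested** (section 4.4, Recruitment and screening for COPD): "The breathing assessment will include a validated symptom-based questionnaire and in those that are symptomatic the following". The list covers spirometry, a chest radiograph and a full blood count.
- **Case definition** (same place): "A fixed post bronchodilator FEV1/FVC ratio <0.7 will be used to establish the diagnosis of COPD as per GOLD guidance".
- **Target** (section 3.2): "Determine the actual prevalence of undiagnosed COPD in an underserved primary care populations (WP2". Nothing restricts it to symptomatic disease.
- **Sample size** (section 4.4): "The two PCN patient registers will be randomly sampled to obtain 4,761 people >35year"; "Anticipating a 30% uptake, 1,428 people will undergo a breathing assessment"; "assuming a 7% prevalence, a cohort of 100 patients with COPD from underserved communities will be recruited".
- **Data** (section 11.1.3): prevalence data are to exist for every participant.
- **Use of the result** (section 4.4, Sample size): WP2 is to be compared with, and to validate, the WP1 model estimates, and to be compared with registered diagnoses on the QOF register.
- **Benchmark for WP1** (section 4.3, Data Analysis): the model is also compared with a national health survey that "included a subset of people who underwent spirometry to diagnose COPD".

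The protocol does not provide for spirometry in any screen-negative attendee, for a correction for questionnaire sensitivity, or for a target limited to symptomatic COPD.

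**The concern.** A case exists only where the ratio has been measured, and it is measured only after a positive symptom screen. Airflow obstruction in a screen-negative attendee cannot be found. The objective and the 7% calculation nevertheless read as if COPD status were known for everyone assessed. Together with the statement in section 11.1.3, this implies that untested attendees count as non-cases.

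The study asks whether COPD burden is under-estimated in underserved populations. A survey that can err only downward at this step pushes its answer in the same direction as the problem under study. If its estimate falls below the WP1 model's, a reader could not tell whether the model is too high or the survey has missed cases without symptoms.

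**Working it through.** **Inputs.** From the Sample size paragraph: 4,761 invited, 30% uptake, 7% prevalence. From the screening paragraph: spirometry only if symptomatic, and COPD defined by the ratio. Not given, so assumed: *s*, the share of true spirometric cases among attendees who screen symptomatic. It is shown at 0.9, 0.7 and 0.5.

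**1. The plan's own figures.** 4,761 × 0.30 = 1,428.3, and 1,428 × 0.07 = 99.96. The 1,428 and the 100 reproduce. They fit the design only if every case screens positive (*s* = 1) or if 7% already means symptomatic COPD. The protocol does not say which.

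**2. If 7% is the full spirometric prevalence.** Screen-negative attendees stay in the denominator and contribute no cases:

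- observed prevalence = 7% × *s*
- expected cases = 1,428 × 0.07 × *s*
- invitations needed for 100 cases = 100 / (0.30 × 0.07 × *s*)

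| *s* (assumed) | Observed prevalence | Shortfall (points) | Cases | Invitations for 100 cases |
|---|---|---|---|---|
| 0.9 | 6.3% | 0.7 | 90 | 5,291 |
| 0.7 | 4.9% | 2.1 | 70 | 6,803 |
| 0.5 | 3.5% | 3.5 | 50 | 9,524 |

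**3. If 7% already means symptomatic COPD.** The 100 cases stand. Spirometric prevalence among attendees would then be 7% / *s*, which is 7.8%, 10.0% or 14.0% for the same three values. The survey would not see the difference.

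**4. Against sampling error.** The half-width is 1.96 × √(0.07 × 0.93 / 1,428) = 0.0132, or about ±1.3 points. Computed at the observed prevalence, it is slightly smaller for lower *s*. The shortfall 7 × (1 − *s*) exceeds the half-width once *s* is below about 0.83. The protocol states ±4–5 points. That does not reproduce at 1,428 people and is a separate matter. In either case a larger sample narrows the interval without removing the shift.

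**The case against.** **Symptomatic COPD may be what the study intends.** That is possible, and the 100 cases would then stand. But the objective and the sample size paragraph do not say so.

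**Nothing states that untested people are disease-free, and a SAP could settle how they are classified.** The first part is correct: the classification is inferred from the denominator and from section 11.1.3. A SAP could choose a classification or an adjustment. It could not recover measurements that were never taken.

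**The comparators are not all mismatched.** This stands in part. The QOF register holds clinically diagnosed patients and may lie closer to symptomatic disease, so the mismatch there is weaker. A reader might take the national health survey as a comparator of WP2, but section 4.3 sets it against the WP1 model only. WP1 takes its associations from published literature without a stated case definition, so the WP1 mismatch is itself inferred, mainly from that spirometry benchmark.

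**The reference to BOLD.** Section 4.4 describes recruitment "using the Burden of Obstructive Lung Disease (BOLD) methodology", and a reader might infer a departure from it. The protocol does not say who had spirometry in BOLD, so no such departure can be shown from it.

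**Two stronger readings are tempting and are not supported.**

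- At *s* = 0.7 the 4.9% lies near the 4.5% diagnosed figure in section 2.3, so a reader might conclude that most underdiagnosis would vanish. That follows only from crude subtraction (4.9 − 4.5 = 0.4, against 7 − 4.5 = 2.5). If the same 70% applies to undiagnosed cases, 2.5 × 0.7 = 1.75 points are found, a loss of 30%. The 4.5% is also a UK figure for people over 40, whereas WP2 samples people over 35 in two deprived networks.
- Interpreters are planned, so a reader might expect false differences between language groups. Sensitivities of 80% and 60% would turn an equal 7% into 5.6% and 4.2%. Those sensitivities are invented, and the protocol sets out no WP2 comparison by language. With two groups of 714, the half-width of the difference is 1.96 × √(0.056 × 0.944/714 + 0.042 × 0.958/714), about ±2.2 points, so the 1.4-point gap lies within sampling error. Differential sensitivity is possible but undocumented.

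**Conclusion.** The point holds in a limited form. As designed, WP2 estimates the prevalence of symptomatic (screen-positive) COPD among attendees. It cannot deliver the unqualified target in section 3.2, and the 7% behind the 100 cases has no stated definition.

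If 7% is full spirometric prevalence, questionnaire sensitivity of 90% to 50% would give an observed 6.3% to 3.5% and 90 to 50 cases. The size rests entirely on that assumed range. The direction follows from the design: any sensitivity below 100% lowers the estimate relative to spirometric prevalence among attendees. The main consequence is for the planned validation of WP1. The consequence for the QOF comparison is smaller.

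**What to change.** These changes are to wording and reporting and need no extra procedures:

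1. In section 3.2 and the Sample size paragraph, name the WP2 estimand as the prevalence of symptomatic COPD: screen-positive and ratio below 0.7. Align section 11.1.3 by saying how untested attendees are classified.
2. State that this is a lower bound for spirometric COPD among attendees.
3. Say which definition the 7% refers to, and restate the expected number of cases to match.
4. Do not use the estimate unadjusted to validate WP1 estimates of all spirometric COPD. Either put WP1 on the same definition, or present a sensitivity analysis over a stated range of questionnaire sensitivity.
5. Report the proportion screening positive, overall and by registered language.

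Spirometry in a random subsample of screen-negative attendees, weighted back, is optional. It needs extra procedures within a team whose capacity section 4.4 already treats as limited, and it would measure sensitivity imprecisely. As an illustration, assume 35–50% screen positive and 70% sensitivity. About 928 to 714 attendees are then screen-negative (1,428 × 0.65 and 1,428 × 0.50), with some 30 missed cases among them. Testing 200 would find about 6 to 8 (200/928 × 30 = 6.5; 200/714 × 30 = 8.4). The overall half-width would be about ±1.8–1.9 points.

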## Data management:

Data will be pseudonymised and collected using REDCap, a secure web-based application supporting electronic data capture. Data will be held on a secure server with a back-up schedule. Data will only accessible via the University of Sheffield encrypted network and all extracts and entries logged via REDCap audit trail. A data manager will set up REDCap and be involved in clinical records form development. They will continue to carry out server maintenance for the duration of the clinical study. Data will be cleaned and exported for further downstream analysis in R, always held on secure university storage and approved devices.

#### 4.5 Qualitative semi-structured interviews (WP3-4)

## Recruitment:

Using purposive sampling of general practices within The Foundry and SAPA5 PCNs, we will recruit 10-15 health care workers (General practitioners, Practice Managers, Practice Nurses, Advanced Nurse Practitioners, Health Care Assistants, Care Coordinators, and Physicians Associates). This number might vary according to emerging findings and through an on-going iterative process.

Purposive sampling informed by the findings from WP1 & 2 will recruit 15-25 people with lived experience of COPD (subject to data saturation) from underserved populations. Purposive sampling will be informed by factors such as general practice registration, age, sex, deprivation, non-english speaking, and ethnicity. We will seek to include patients for whom language/literacy is often a barrier in-line with Include NIHR guidance.46

